5.1 ENTRY CRITERIA

5.1.1 Inclusion Criteria

Subjects must meet all of the following criteria:

1. Age 18 years or older.
2. Subjects who have been diagnosed with indolent NHL [defined as FL, MZL (splenic, nodal and extranodal), or SLL] that has progressed.
 - a. For subjects for whom the most recent biopsy was performed >36 months before the first dose of IPI-145, a repeat biopsy to confirm histology should be performed, unless medically contraindicated.
 - b. For subjects who progressed within 2 months of initiating last prior chemotherapy, a repeat biopsy to confirm histology should be performed, unless medically contraindicated.
3. Subjects must have disease that is refractory to a chemotherapy regimen or RIT. The chemotherapy regimen (with or without rituximab) must contain at least one alkylating agent or purine nucleoside antagonist. See Appendix 5 for examples of suitable prior chemotherapy.

Refractory is defined as either:

- a. Lack of a CR or PR while receiving the chemotherapy regimen or RIT
or
- b. PD within 6 months of the last dose of the chemotherapy regimen or RIT documented by CT, PET/CT or MRI obtained within 6 months after the last dose

Note: Subjects exhibiting clinical progression within 6 months after the last dose of a chemotherapy regimen or RIT who are unable to undergo CT, PET/CT or MRI within the 6 month timeframe are allowed up to an additional 30 days to confirm radiologic progression.

4. Subjects must have disease that is refractory to rituximab. Refractory is defined as any of the following:
 - a. Lack of a CR or PR during treatment with a full course of single-agent rituximab (≥ 4 doses of 375 mg/m^2 , weekly) or ≥ 2 doses of $\geq 375 \text{ mg/m}^2$ of rituximab in combination with chemotherapy
 - b. PD within 6 months of the last dose of a full course of single-agent rituximab or rituximab in combination with chemotherapy

c. PD during, or within 6 months of the last dose of a rituximab maintenance therapy

5. Measurable disease with a lymph node or tumor mass ≥ 1.5 cm in at least one dimension by CT, PET/CT or MRI.
6. Eastern Cooperative Oncology Group (ECOG) performance status 0-2 (corresponds to Karnofsky Performance Status [KPS] $\geq 60\%$).
7. Adequate renal function, defined as serum creatinine $\leq 2 \times$ upper limit of normal (ULN).

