CR	Disappearance of all evidence of disease	a) FDG-avid or PET positive prior to therapy: mass of any size permitted if PET negative b) Variable FDG-avid or PET negative prior to therapy: regression to normal size on CT	Not palpable, nodules disappeared	Infiltrate cleared on repeat biopsy; if indeterminate by morphology, immunochemistry should be negative
PR	Regression of measurable disease and no new sites	≥50% decrease in SPD of up to 6 largest dominant masses; no increase in size of other nodes a) FDG-avid or PET positive prior to therapy: one or more PET positive at previously involved site b) Variable FDG-avid or PET negative: regression on CT	≥50% decrease in SPD of nodules (for single nodule in greatest transverse diameter); no increase in size of liver and spleen	Irrelevant if positive prior to therapy; cell type should be specified
SD	Failure to attain CR/PR or PD	a) FDG-avid or PET positive prior to therapy: PET positive at prior sites of disease and no new sites on CT or PET b) Variable FDG-avid or PET negative; no change in size of previous lesions on CT		
Relapsed disease or PD	Any new lesion or increase by ≥50% of previously involved sites from nadir	Appearance of new lesion(s) >1.5 cm in any axis, ≥50% increase in SPD from nadir of more than one node, or ≥50% increase in longest diameter of a previously identified node >1 cm in short axis Lesions PET positive if FDG-avid lymphoma or PET positive prior to therapy	>50% increase from nadir in the SPD of any previous lesions	New or recurrent involvement

Abbreviations: CR, complete remission; FDG, [¹⁸F] fluorodeoxyglucose; PET, positron emission tomography, CT; computed tomography; PR, partial remission; SPD, sum of the product of the diameters; SD, Stable disease; PD progressive disease.

Adverse events, including SAEs, associated with any disease assessment must be collected per [Section 8.2.1](#).

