9.3 ANALYSIS SETS

The Full Analysis Set (FAS) will include all subjects who were treated with at least one dose of IPI-145. The FAS will be the primary analysis set for all efficacy and safety analyses.

The Evaluable Analysis Set (EAS) will include all subjects who had no major protocol violations and who remained in the treatment phase of the study for at least 8 weeks with an adequate baseline tumor assessment and at least 1 adequate post baseline tumor assessment. Subjects with documented disease progression before 8 weeks of treatment should be considered as “early progression” subjects and, therefore, should be considered evaluable. The EAS will be a secondary analysis set for selected efficacy analyses.

Major protocol violations include failure to satisfy key entry criteria, or taking other anticancer therapies or other prohibited medications during the treatment phase of the study that could seriously confound the effects of the study treatment.

For each of the above two analysis sets, subsets defined by disease subtypes will be identified so that efficacy analyses for disease subtypes can be performed.

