4.2 EVALUABLE ANALYSIS SET

The Evaluable Analysis Set (EAS) will include all subjects who meet the following criteria:

- Remain in the treatment phase of the study for at least 8 weeks or have a documented disease progression per revised IWG criteria before 8 weeks of treatment
- Have an adequate baseline tumor assessment (at least one nodal target lesion ≥ 1.5 cm in the longest diameter)
- Have at least 1 adequate post baseline tumor assessment unless death due to disease progression
- No major protocol deviations that could have an impact on efficacy (The following list is phrased in terms of deviations. Subjects meeting these conditions will be excluded from the EAS):
 - Have not been diagnosed with indolent NHL [FL, MZL or SLL] (inclusion criterion #2)
 - Do not have disease that is refractory to a chemotherapy induction regimen or RIT (inclusion criterion #3)
 - Do not have disease that is refractory to rituximab (inclusion criterion #4)
 - Prior treatment with any PI3K inhibitor or Bruton's Tyrosine Kinase (BTK) inhibitor (exclusion criterion #2)
 - Grade 3B FL and/or clinical evidence of transformation to a more aggressive subtype of lymphoma (exclusion criterion #7)
 - Have been taking other anticancer therapies during the treatment phase of the study that could seriously confound the effects of the study treatment

The EAS will be a secondary analysis set for selected efficacy analyses.

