5.3 EXPLORATORY EFFICACY ENDPOINT

The exploratory efficacy endpoint of this study is:

- Lymph node response rate (LNR rate), with LNR defined as $\geq 50\%$ reduction in the Sum of the Products of the Perpendicular Diameters (SPD) of nodal target lesions

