7.2.1 Analysis of Primary Efficacy Endpoint

7.2.1.1 Primary Analysis

ORR will be tested against the null ($\leq 30\%$) by 1-sided exact binomial test at 0.025 level. The estimated ORR (percent of subjects with a BOR of CR or PR), a 2-sided 95% exact confidence interval and the p-value will be provided. Number and percentage of subjects with BOR in each of the response categories (CR, PR, SD, PD, NED and UNK) will also be presented. All subjects in the analysis set will be included in the denominator in the calculation of the percentage for each response category or ORR. In other words, missing data will be imputed for the calculation of ORR by assuming that any subjects not exhibiting a response (CR or PR) are non-responders.

Best overall response (BOR) and ORR will be presented for the overall population. They will also be presented for the FL population, as well as other disease subtypes (MZL and SLL). For each disease subtype, the summary will be the same as that for the overall population except that the hypothesis test will not be performed.

ORR will be analysed for the subgroups provided in [Section 6.5](#). These subgroup analyses will also be performed similarly for FL subjects. A forest plot of ORR for different subgroups will also be provided.

Listings of data to support response assessment, including lesions with dimensions, liver/spleen assessments, bone marrow and B symptoms will be provided.

These analyses will be performed for the FAS and the EAS with FAS being the primary analysis set.

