7.2.3 Analyses of Exploratory Efficacy Endpoint

7.2.3.1 LNR Rate

The estimated LNR rate will be provided together with a 2-sided 95% confidence interval. A waterfall plot of the best percent change in the SPD of nodal target lesions will also be provided. Only subjects with baseline and post-baseline nodal target lesion measurements will be included in the plot.

LNR rate will be analysed for the FAS and the EAS with FAS being the primary analysis set. It will also be analysed for the FL population, as well as the other disease subtypes within the FAS.

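### Two minor SAP corrections: the EAS baseline rule in 4.2 is narrower than inclusion criterion 5, and Table 2 row 1 censors PFS deaths that row 5 counts as events

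*SAP*

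**What the plan says.** **EAS baseline.** SAP 4.2 lists the conditions for the EAS. One reads "Have an adequate baseline tumor assessment (at least one nodal target lesion", with a minimum longest diameter of 1.5 cm. Protocol 9.3 asks for treated subjects "with an adequate baseline tumor assessment and at least 1 adequate post baseline tumor assessment" and does not define adequate.

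Entry is wider. Inclusion criterion 5 (Protocol 5.1.1) requires "Measurable disease with a lymph node or tumor mass" of at least 1.5 cm in one dimension. Inclusion criterion 2 covers indolent NHL, "defined as FL, MZL (splenic, nodal and extranodal), or SLL] that has progressed".

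The EAS is a secondary set. For ORR, SAP 7.2.1.1 says "These analyses will be performed for the FAS and the EAS with FAS being the primary analysis set", and that section includes ORR by disease subtype (FL, MZL, SLL) and by subgroup. PFS, DOR, OS, TTR and lymph node response (LNR) rate are also repeated in the EAS, but their subtype analyses stay within the Full Analysis Set (FAS).

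**PFS censoring.** SAP 5.2 counts death from any cause as a PFS event. In SAP Table 2 (section 7.2.2.1):

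- Row 1: no adequate baseline assessment; censored at first dose. No exception for death.
- Row 2: no adequate post-baseline assessment; censored the day after first dose. Carries an exception for death.
- Row 5: death before documented progression with at most one missed scheduled assessment; event at date of death. No condition on baseline.

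A note limits rows 1 and 2 to PFS. No order of precedence between rows is stated.

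**The concern.** An evaluable set should remove subjects whose response cannot be judged. As written, SAP 4.2 also removes subjects because of where their lesion lies. A subject with extranodal MZL and one measurable extranodal mass meets every entry criterion and may be assessable under the IWG criteria, yet fails the EAS condition. The loss would fall mainly on MZL, for which the SAP plans a separate EAS response rate. An EAS result that differs from the FAS result could then reflect lesion site rather than evaluability.

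In Table 2, a subject with no adequate baseline who dies before progression, with at most one missed assessment, fits both row 1 (censored) and row 5 (event). Two programmers could code that subject differently. The row 1 choice removes a death from an endpoint defined to include deaths, and can only flatter the PFS estimate.

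**Working it through.** **1. The plan's own figure.** Inputs from SAP 3.2 and 3.4: n = 120, null ORR 30%, alternative 45%, one-sided alpha 0.025, futility stop at 7 or fewer responders of 30. The exact binomial critical value is 47 of 120. P(X ≥ 47) is 0.0200 at 30% and 0.916 at 45%. With the futility stop observed, alpha is 0.0195 and power 0.910. The stated power above 90% is reproduced. The test uses the FAS, which takes in every treated subject, so neither correction changes it.

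**2. Does nodal mean lymph node?** SAP 5.3 defines LNR as at least a 50% "reduction in the Sum of the Products of the Perpendicular Diameters (SPD) of nodal target lesions". The same phrase there describes lymph node response, so the natural reading in 4.2 is lymph nodes only.

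**3. Is a nodal lesion needed to assess response?** Protocol Table 8 has a separate spleen and liver column. For PR it asks for at least a 50% "decrease in SPD of nodules (for single nodule in greatest transverse diameter"). A subject without a nodal target lesion can therefore be assessable.

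**4. Size of the EAS effect.** Let m be the number of extranodal-only subjects, which the documents do not give. Assume N = 120, ORR of 45% in the others, ORR of 25% or 65% in these m, and no other EAS exclusions.

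- ORR with them kept: [(N − m) × 0.45 + m × p]/N. ORR with them dropped: 0.45.
- Shift = m × |0.45 − p|/N = m × 0.20/120.
- m = 1: 0.17 points; m = 3: 0.50; m = 6: 1.00; m = 12: 2.00. The sign depends on whether p is above or below 45%.

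For comparison, the exact 95% interval at 54/120 is 35.9% to 54.3%, which is 18.4 points wide.

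Outer limits, holding 54/120 responders overall and letting all or none of the m respond:

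- m = 1: 53/119 to 54/119, or 44.5% to 45.4%.
- m = 3: 51/117 to 54/117, or 43.6% to 46.2%.
- m = 6: 48/114 to 54/114, or 42.1% to 47.4%.
- m = 12: 42/108 to 54/108, or 38.9% to 50.0%.

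**5. Size of the Table 2 effect.** Let j subjects with no adequate baseline die before a landmark, let S be landmark PFS in the other 120 − j, and assume no other censoring.

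- Row 1 gives S. Row 5 gives S × (120 − j)/120.
- Difference = S × j/120.
- j = 1: 0.4 × 1/120 = 0.33 points; 0.7 × 1/120 = 0.58 points.
- j = 3: 0.4 × 3/120 = 1.00 point; 0.7 × 3/120 = 1.75 points.

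Both j and the range of S (40% to 70%) are assumptions.

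**The case against.** **Nodal may be shorthand.** The 4.2 condition uses the same 1.5 cm threshold as inclusion criterion 5, and criterion 5 is absent from the deviation list in 4.2. Table 8 has no column for an extranodal mass outside liver, spleen and marrow, so such a mass could be scored only as a dominant mass under the nodal column. On that reading fewer subjects, perhaps none, would be lost. The reading is possible, but 4.2 does not state it and SAP 5.3 points the other way, so the wording still needs correcting.

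**The upper counts are generous.** Protocol 1.2.2 puts SLL, MALT-type and nodal MZL at about 6%, 5% and 1% of B-cell lymphomas. As a rough guide (splenic MZL is not given, and a refractory population may differ), MALT-type would be 5/12 of the 40 or so non-FL subjects, about 17. Twelve extranodal-only subjects would then be about 70% of them (12/17). This stands: m = 12 is an outer value, not an expectation.

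**Row 1 will rarely apply.** Measurable disease is an entry criterion and screening CT is required for all subjects, so few can lack an adequate baseline, possibly none. It can also be argued that row 1 is the more specific rule and comes first. The rarity stands. The precedence argument does not, because the table gives no order and the result conflicts with SAP 5.2.

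**Stronger readings that a reader might infer:**

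- That 4.2 contradicts the protocol. Protocol 9.3 leaves adequate undefined, so the SAP narrows the term.
- That the nodal test carries into the primary ORR or into Table 2. SAP 5.1 allows an adequate baseline showing no evidence of disease, so the word has a different meaning there, and Table 2 does not refer to 4.2.
- That a large effect follows in a pooled non-FL group. SAP 7.2.1.1 reports MZL and SLL separately; no pooled summary is planned.
- That 4.2 dilutes the LNR rate. SAP 7.2.3.1 says "LNR rate will be analysed for the FAS and the EAS with FAS being the primary analysis set". Under the current rule every EAS subject has a nodal lesion, and subtype LNR is run within the FAS, which 4.2 does not touch.

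**Conclusion.** Both points hold on the text, are independent of each other, and are low priority.

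1. SAP 4.2 is narrower than the entry criterion. Read literally, it drops eligible, assessable subjects from the secondary EAS analyses, including EAS ORR for MZL. The overall EAS ORR shift is about 0.2 to 2.0 points in either direction, given 1 to 12 such subjects and a 20-point difference in response rate, both assumed. This is small against an 18.4-point interval.

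2. Table 2 row 1 conflicts with row 5 and with the PFS definition. The effect is on FAS PFS only: about 0.3 to 1.8 points upward for an assumed 1 to 3 deaths. EAS PFS is untouched because the EAS requires an adequate baseline. DOR, OS and ORR are also untouched, and the deaths still count in OS.

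The primary FAS ORR, alpha and power do not change. Confidence in the size is limited because the documents give neither count.

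**What to change.** - **SAP 4.2:** replace the nodal condition with at least one measurable nodal or extranodal lesion of at least 1.5 cm, matching inclusion criterion 5.
- **SAP 7.2.3.1:** because that change widens the EAS, state that the EAS LNR rate is computed in subjects with a baseline nodal target lesion. Otherwise the wider set would include subjects who cannot have a lymph node response.
- **SAP Table 2, row 1:** add an exception for death, as row 2 has, so that row 5 applies.

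The cost is three short wording changes with minor reprogramming of the EAS flag, the EAS LNR denominator and the PFS derivation. There are no new data and no change to sample size, alpha or the primary analysis. The changes should be settled before the final analysis, so that the choices are not made with results in view.

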5 STUDY ENDPOINTS AND OTHER VARIABLES

5.1 PRIMARY ENDPOINT

The primary endpoint for the study is ORR, with overall response defined as best response of complete response/remission (CR) or partial response/remission (PR), according to the revised IWG Criteria.

ORR will be derived from best overall response (BOR), which is defined as the best time-point response that a subject achieves during the course of the study, with the response ranked according to the following order (from best to worst): CR>PR>SD>PD. In addition, a subject who does not have an adequate baseline assessment or who does not have any adequate post-baseline response assessment will have a BOR of unknown (UNK). A subject who has an adequate baseline assessment that shows no evidence of disease and who does not have a post-baseline assessment of PD will have a BOR of no evidence of disease (NED).

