6.3.13 Indolent NHL Response Assessments

All disease specific assessments are to be completed (see [Table 8](#)) and as outlined in [Table 3](#). The modality chosen to evaluate each individual subject should be the same throughout the duration of the study. Copies of all scans will be sent for independent review of response assessment.

CT scans of the chest, abdomen and pelvis are required for all subjects at Screening. These assessments may be performed within 7 days of initiating the next cycle of therapy (Day -7 to Day 1) of Cycles 3, 5, 7, 10, 14 and every fourth Cycle thereafter (Cycle 18, 22, etc.) until disease progression or start of other anticancer therapy. Copies of all scans will be sent for independent review of response assessment. Other scans may be performed (e. g, neck/head CT) if clinically indicated or if the area is a site of known disease. MRI may be substituted if clinically indicated, but the modality chosen to evaluate each individual subject should be the same throughout the duration of the study. The frequency outlined is the minimum required for study participation.

Scans will be performed at the EoT if the subject is discontinued for reasons other than radiological disease progression and a previous assessment has not been performed within 30 days of the EoT visit. If the subject has discontinued treatment for reasons other than disease progression, scans should be performed until disease progression or start of additional anticancer therapy (see [Table 3](#) for scan frequency).

Bone marrow biopsy and/or bone marrow aspirates are to be performed at Screening (where clinically indicated) and as required thereafter to confirm a complete response as per the revised IWG criteria.¹ If the screening samples are performed within 60 days of Cycle 1, Day 1 and frozen aspirate sample and unstained slides or blocks are available, these results can be used in place of the Screening assessment. If bone marrow aspirate and/or bone marrow biopsy is performed, the Screening and the post-Screening bone marrow biopsies and/or aspirate samples should be sent for biomarker analysis if available. See the IPI-145-06 Laboratory Manual for further instructions regarding the handling, shipping, and storage of the samples.

[Table 8](#) shows the major criteria employed for disease response assessment.

Table 8: Disease Response Criteria

Response	Definition	Nodal Masses	Spleen Liver	Bone Marrow

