3.2 SAMPLE SIZE CONSIDERATION

The primary endpoint of the study is overall response rate (ORR), as defined in [Section 5.1](#). This study will test the null hypothesis that the ORR is $\leq 30\%$ against the alternative that ORR is $\geq 45\%$. Using a group sequential design with 1 interim analysis, 120 subjects will provide $>90\%$ power to achieve a one-sided overall significance level of 0.025. The interim analysis will occur approximately 4 months after at least 30 subjects (25% of the total) have initiated treatment with IPI-145. The cumulative Type II error to be spent at the interim and final analyses are 0.02 and 0.1, respectively. The interim analysis is intended for futility only and hence no Type I error will be spent.

Among the 120 subjects to be enrolled, approximately 80 will be FL.

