5.2 SECONDARY EFFICACY ENDPOINTS

The secondary efficacy endpoints of the study are:

- Duration of response (DOR) defined as the time from the first documentation of response to the first documentation of progressive disease (PD) or death due to any cause
- Progression-free survival (PFS) defined as the time from the first dose of study treatment to the first documentation of PD or death due to any cause
- Overall survival (OS) defined as the time from the first dose of study treatment to the date of death
- Time to response (TTR), defined as the time from the first dose of study treatment to the first documentation of response (complete or partial)

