7.2 EFFICACY ANALYSES

Assessment of response and progression status will be evaluated locally (i.e. Investigator's assessment) and by an independent, third party panel of radiologists and oncologists (Independent Review Committee [IRC]) according to the revised IWG Response Criteria for Malignant Lymphoma¹. The IRC assessment will be used for the primary analyses of response and progression-based efficacy endpoints (e.g., ORR, PFS, TTR and DOR). Data based on local assessment will also be presented for these endpoints.

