7.2.2 Analyses of Secondary Efficacy Endpoints

7.2.2.1 Progression Free Survival (PFS)

Censoring of PFS will be performed as detailed in Table 2 below. Note that progression may be documented based on scheduled or unscheduled disease status assessment, and that unscheduled disease status assessment may be included in calculating the gap between adequate disease status assessments.

PFS will be presented using the Kaplan-Meier method. A 2-sided 95% confidence interval for median PFS will be provided. PFS will be analysed for the FAS and the EAS with FAS being the primary analysis set. It will also be analysed for the follicular lymphoma population, as well as the other disease subtypes within the FAS.

Table 2: PFS and DOR censoring algorithm

Situation	Date of Event or Censoring	Outcome
No adequate baseline disease status assessment	Date of first dose	Censored
No adequate post-baseline disease status assessment unless death occurs prior to first post-baseline assessment	Date of first dose + 1	Censored
No documented progression or death before data cutoff	Date of last adequate disease status assessment	Censored

Situation	Date of Event or Censoring	Outcome
Documented progression with ≤ 1 missing scheduled disease status assessment before progression	Date of the earliest assessment that results in a finding of unequivocal progression	Event
Death before progression being documented with ≤ 1 missing scheduled disease status assessment before death	Date of death	Event
Documented progression or death following a long gap between adequate disease status assessments (e.g., 2 or more consecutive missed scheduled disease status assessments along with a gap of more than 6 months)	Date of last adequate disease status assessment before the gap	Censored
New anticancer treatment or procedure started before documented progression	Date of last adequate disease status assessment	Censored

Note: the first two rows are applicable to PFS only.

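### Best overall response is not cut off at first progression, so an IRC response read after IRC progression counts in the primary ORR but falls after the PFS event

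*SAP*

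**What the plan says.** SAP 5.1 bases ORR on best overall response (BOR), "which is defined as the best time-point response that a subject achieves during the course of the study", with CR ranked above PR, PR above SD, and SD above PD. Only the category for no evidence of disease depends on the absence of PD; CR and PR carry no such condition. SAP 7.2.1.1 counts a subject as a responder if BOR is CR or PR. Protocol 3.1 and 9.4.1 add no time limit.

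SAP 7.2 fixes the assessor: "The IRC assessment will be used for the primary analyses of response and progression-based efficacy endpoints". Investigator reads are also presented.

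The time-to-event endpoints do stop at progression. SAP 5.2 defines DOR as "the time from the first documentation of response to the first documentation of progressive disease" or death. SAP Table 2, which serves PFS and DOR, dates the event at "Date of the earliest assessment that results in a finding of unequivocal progression" and censors when new anticancer treatment starts before progression.

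On conduct, Protocol 4.4 lists progression as a reason to stop treatment. Protocol 6.3.13 schedules scans "until disease progression or start of other anticancer therapy", and Protocol 6.5.2 and Table 4 stop follow-up assessments on similar terms. Copies of all scans go to independent review.

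**The concern.** Under the ranking in SAP 5.1, any PR or CR overrides a PD whichever came first. PFS and DOR work from the first PD. All three endpoints come from the same IRC reads in the primary analysis, so one subject can be a responder in ORR and, at an earlier date, a progression event in PFS.

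The primary numerator could then hold subjects whom the IRC had already called progressed, with no settled rule for their DOR. Relative to the usual meaning of ORR, response before progression, the error goes only upward. The trial is single-arm, open-label and tested against a fixed 30%, so no control arm would absorb it. If such cases appear, someone must decide how to score them after seeing the data.

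**Working it through.** **1. Can it happen under the text?** Take IRC PD at the Cycle 3 scan, no local PD, continued treatment, and IRC PR at the Cycle 5 scan.

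| Rule | Result for this subject |
|---|---|
| SAP 5.1, 7.2.1.1 | BOR = PR; responder |
| SAP 5.2, Table 2 (PFS) | Event at Cycle 3 |
| SAP 5.2, 7.2.2.2 (DOR) | Starts at Cycle 5; first PD at Cycle 3, so negative or undefined |

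The stopping rules in Protocol 4.4, 6.3.13 and 6.5.2 name no assessor and describe no IRC confirmation of PD, so they do not exclude this subject. Protocol Table 8 narrows the route, because PR requires no new sites. It does not close it, because PD can be met without a new site, by a sufficient "increase in longest diameter of a previously identified node".

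**2. Does a planned analysis catch it?** No. The sensitivity analysis in SAP 7.2.1.2 concerns lymphocytosis in SLL. The EAS (SAP 4.2) keeps subjects who progress before 8 weeks and has no exclusion for response after PD.

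**3. Reproducing the design.** Inputs from SAP 3.2 and 7.2.1.1: N = 120, null 0.30, alternative 0.45, one-sided exact binomial test at 0.025. With X ~ Bin(120, p):

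- P(X ≥ 46 | 0.30) = 0.0312: fails; 46/120 has a lower 95% limit of 29.6%.
- P(X ≥ 47 | 0.30) = 0.0200: passes; 47/120 has a lower 95% limit of 30.4%.
- P(X ≥ 47 | 0.45) = 0.916. With the futility stop at 7 or fewer of 30 enforced (SAP 3.4), power is 0.910 and alpha 0.0195.

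This agrees with the plan's claim of more than 90% power.

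**4. Size under assumed counts.** The documents give no number of subjects whose only IRC response follows IRC PD. Call it k, and let the other 120 − k respond at 30%.

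- Counted: P(X ≥ 47 − k), X ~ Bin(120 − k, 0.30).
- Not counted: P(X ≥ 47), same distribution.

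| k (assumed) | Success if counted | Success if not counted |
|---|---|---|
| 0 | 0.020 | 0.020 |
| 1 | 0.027 | 0.017 |
| 2 | 0.036 | 0.014 |
| 3 | 0.047 | 0.012 |

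These are not type I errors. For k = 2 the expected ORR is (2 + 0.30 × 118)/120 = 31.2% if counted and 0.30 × 118/120 = 29.5% if not, so the columns lie on either side of the null. For ORR exactly as the SAP defines it, the test's error stays 0.020.

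**5. When does one such subject decide the trial?** Only if the other 119 give exactly 46 responders, P(X = 46), X ~ Bin(119, p):

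| p | Probability |
|---|---|
| 0.30 | 0.010 |
| 0.35 | 0.053 |
| 0.40 | 0.072 |
| 0.45 | 0.028 |

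**The case against.** The strongest reply is that the event is rare. It needs IRC PD without local PD, continued treatment, no IRC response before that PD, and then an IRC PR or CR, all in one subject. Table 8 also requires no increase in other nodes for a PR and measures nodal progression from nadir, so the node that grew must itself regress. Protocol 1.5 reports a median time to response of 1.8 months (range 1.5 to 4.1) in the earlier iNHL cohort, which leaves little room for progression first and response second if that pattern carries over. An IRC charter may stop reads at PD. DOR can be computed if its end is read as the first PD after response. Nothing in the documents supports k = 2 or 3.

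All of this bears on frequency, and it stands: the effect may be nil, and the counts above are illustrative. It does not supply the missing rule. Neither document says that IRC reading stops at PD. Reading DOR as ending at a later PD would give DOR and PFS different first progressions, although both use Table 2, which takes the earliest. A requirement that progression be unequivocal could exclude some PD reads that later reverse, but the SAP does not say how.

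Responses after new anticancer therapy are a smaller exposure. Protocol 6.3.8.8 prohibits such therapy on treatment, scheduled scans end when it starts, and the EAS drops subjects it seriously confounds. Only deviations or off-schedule scans in the FAS remain.

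**Conclusion.** The concern holds. Followed literally, SAP 5.1 counts an IRC response read after IRC PD in the primary ORR, while the PFS rule has already recorded an event from the same reads and DOR has no usable value unless a different PD is chosen. ORR changes only for subjects with no IRC response before their IRC PD, and then only upward. Their number cannot be derived from the documents and may be zero. Given one such subject, the chance that the subject decides the outcome is about 1% to 7% over response rates of 30% to 45%. This is a defect in the endpoint definition. The exact test, the 47/120 threshold and the stated power are all sound. It should be corrected, with medium confidence that it will matter in practice, because IRC procedures outside these documents might already prevent it.

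**What to change.** In SAP 5.1, define BOR as the best time-point response from first dose up to and including the first PD by the same assessor, and before the start of any new anticancer therapy. The assessor is the IRC for the primary analysis and the investigator for the supportive one. Apply the same window to TTR and DOR, and list any later responses separately. In the last row of SAP Table 2, state that the censoring date is the last adequate assessment before the new treatment.

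The cost is one sentence in SAP 5.1 and one phrase in Table 2. N = 120, the 47/120 threshold and the power of 0.916 (0.910 with the futility stop) stay as they are. The reported ORR may be slightly lower.
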